15.2.2 IMP related adverse events symptoms

Following vaccination with IMP, diary card symptoms are not reported as individual adverse events unless they are deemed to be clinically significant (i.e. progress past 7 days) in the opinion of the investigator and / or SME.

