9.2 Vaccination Phase

9.2.1 Visit 2 - Day -43

The first vaccine or placebo administration will take place on Day -43, 43 days prior to virus challenge. Study procedures will be conducted as detailed on the Time and Events, table 9.2

Once it is determined that the participant still meets Inclusion/Exclusion criteria for the research study, participants will receive the first of two injections of FLU-v 500mcg+adjuvant 2 doses, FLU-v 500mcg 1 dose + 1 dose placebo , or 2 doses of placebo. The study team will thoroughly discuss the consent with the volunteer. The study team will issue and explain the completion of self-reported adverse events in a 21-day diary card. This diary card will be used to record vaccine-related local and systemic events post first vaccination.

9.2.2 Visit 3 - Day -22 (minimum 21 days post first vaccination +7 days)

The second study drug administration will take place if the participant continues to meet all inclusion and none of the exclusion criteria. Study procedures will be conducted as detailed on the Time and Events schedule

The study team will issue and explain the completion of self-reported adverse events in a 21-day diary card. This diary card will be used to record vaccine-related local and systemic events post second vaccination.

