13.1.7 Adverse events

Adverse events will be recorded from the point of signature of the Informed Consent Form (ICF) to the last study follow-up visit (see Section 15).

Subjects will record any symptoms that they experience after administration of the IMP. These symptoms will be classified as AEs and graded by the Investigator/research nurse according to the tables provided in Appendix 4: Division of Microbiology and Infectious Diseases (DMID) Adult Toxicity Table November 2007 as a reference.

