13.2.3 Adverse events diary cards (Diary report cards)

To look at expected (solicited) local and systemic signs of reactogenicity, 2 AE diary cards will be issued to all study subjects. The cards will need to be completed by the subjects from Day -43 and returned on D-22 and D-2 or D-1. In the event of missing diary card data, the physician will review the AE diary cards in retrospect, and complete the information as accurately as

possible by asking the subject about any symptoms during the missing day. No protocol deviation will be recorded for the missing diary card data.

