18.4.1 Stopping criteria

The study will be terminated if:

- One or more subjects experience any drug related SAEs or 2 or more subjects experience severe or clinically significant AEs considered to be at least possibly related to the FLU-v-004 therapy.
- One or more subjects experience any severe or clinically significant illness from Influenza inoculation.

The PI and the SME will perform safety reviews on available clinical and virology data as appropriate during the quarantine period.

Three clinical scenarios relating to the incidence of AEs and SAEs during the study and the procedures that should be performed in each case are presented in Table 18-1: Study stopping criteria.

Table 18-1: Study stopping criteria

Status	Criterion	Procedure
1	A report has been received of one (or more) IMP-related SAEs in any one (or more) subject(s).	If such a status occurs at any point during the study then further administration of IMP will not take place and the PI and the SME will review the data and make decisions on study continuation or termination. Subject follow-up should continue until resolution or stabilisation of AEs.
2	No IMP-related SAEs have been reported but an overall pattern of clinical changes or symptoms exists, attributed to the IMP, which may appear minor or moderate in terms of individual AEs but which collectively represent a concern for safety.	If such a status occurs at any point during the study then the PI and the SME will review the data and make a decision on study continuation or termination. Subject follow-up should continue until resolution or stabilisation of AEs.
3	Virus-related SAEs or virus-related AEs of clinical concern have been reported following Human Viral Challenge.	Subject follow-up should continue until resolution or stabilisation of all such AEs and final follow-up on Day 28 (± 5 d).

In any event, subject follow-up should continue until resolution or stabilisation of AEs and final follow-up on Day 63 (± 5 d). The exception to this would be suspension of the study for an USM (Section 18.2.2).

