5.6 Safety Endpoints (pre- and post-inoculation)

- **Adverse Events:** Adverse event (AE) terms will be coded using MedDRA version 19.1. Treatment emergent AEs (TEAE) will be reported within summary presentations, by MedDRA system organ class (SOC) and preferred term (PT), and by treatment group. An AE will be classified as treatment emergent if the onset date of the AE is on or after the first administration of vaccine. In the case of partial dates being recorded, a conservative approach will be adopted for inclusion of such events within these reporting periods. If a subject experiences more than one AE with the same preferred term (within reporting period being considered) that preferred term will be counted only once in summary presentations. It will be assigned the worst observed severity and the strongest relationship to IMP among those events for summaries in which those characteristics are considered. Summary presentations will be produced for the number and percentage of subjects reporting treatment emergent AEs, AEs by severity, and AEs related to vaccine administration (by relationship). In addition, SAEs and AEs directly resulting in withdrawal from study will be summarised. Summaries

will be separated into pre-inoculation (events reported from the time of first vaccination up to Day 0 prior to time of inoculation) and post-inoculation (Day 0 inoculation time through study completion). AE rates, evaluated between groups to placebo, will be performed using Fishers exact test.

- **Laboratory parameters:** Laboratory parameters (haematology, biochemistry, cardiac enzymes, coagulation and urinalysis) will be presented as a comparison of treatment groups and placebo by No abnormality detected, Abnormal Not Clinically Significant (NCS), Abnormal Clinically Significant (CS) and Not Available. Laboratory values outside the normal range will be identified in subject listings.
- **Physical Examination:** Physical examination findings (Complete Physical Exam and Directed Physical Exam) will be included within subject listings.

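### Two protocol sections disagree on when a diary-card symptom is an AE, so the TEAE tables and one limb of the stopping rule have no single definition

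*Protocol*

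**What the plan says.** **Capture as AEs.** Protocol 13.1.7 sets no threshold: "Subjects will record any symptoms that they experience after administration of the IMP", and "These symptoms will be classified as AEs and graded by the Investigator/research nurse according to the tables provided in Appendix 4". Protocol 15.2.2 does set one: "diary card symptoms are not reported as individual adverse events unless they are deemed to be clinically significant (i.e. progress past 7 days". The rest of that sentence leaves the decision to the opinion of the investigator and/or the Sponsor's Medical Expert (SME).

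**Instrument.** Protocol 9.2.1 describes the card in AE terms: "The study team will issue and explain the completion of self-reported adverse events in a 21-day diary card". Protocol 13.2.3 gives its purpose: "To look at expected (solicited) local and systemic signs of reactogenicity, 2 AE diary cards will be issued to all study subjects".

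**Use of the AE set.** Protocol 16.7.1 and SAP 5.6 call an AE treatment emergent by its onset date alone. SAP 5.6 adds: "AE rates, evaluated between groups to placebo, will be performed using Fishers exact test". Protocol 18.4.1 terminates the study on one or more related SAEs, or if "2 or more subjects experience severe or clinically significant AEs considered to be at least possibly related to the FLU-v-004 therapy". The synopsis version of that limb adds two conditions, same organ class and confirmation by repeat sample.

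**Separate diary reporting.** SAP 5.4 presents diary events by treatment group, event and severity. Tables 14.2.2.11.1 and 14.2.2.11.2 cover the first and second injection, both on the ITT set. SAP Section 5 limits ITT to participants who were vaccinated and challenged, and places those vaccinated but not challenged in the Safety set only.

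**The concern.** Both rules act on the same events, because the diary is the means by which subjects record symptoms after each injection. A short-lived reaction is therefore an AE under one section and not individually reported under the other. TEAE incidence, severity and causality form a stated safety endpoint (Protocol 6.4.1). Protocol 10.1 says that earlier clinical trials gave only a single dose, so this trial is the first source of human data on the second injection.

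Two things are at stake. The pre-inoculation TEAE tables, including those for severe and vaccine-related events (14.3.2.4.1 and 14.3.2.5.1), could hold quite different content with no change in what subjects experienced. And the numeric limb of the stopping rule counts AEs, so its count inherits the same ambiguity for some reactions.

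**Working it through.** The documents give no figure to reproduce here. The check is a comparison of the rules, followed by two illustrations of size.

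**Step 1. Is there a precedence rule?** The AE text in 13.1.7 points to Section 15, but the pointer is attached to the recording period (consent to last follow-up), not to what counts as an AE. Protocol 15.1.1 lists what an AE does not include. That list excludes typical viral symptoms on FLU-PRO, with a reference to 15.2.1, but has no matching exclusion for diary-card symptoms. SAP Section 6 declares no change to the protocol analyses apart from its pre-defined post-hoc ones. None of these settles the matter.

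**Step 2. The two rules case by case** (reaction related to vaccine, recorded on the diary)

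| Reaction | AE under 13.1.7 | Individual AE under 15.2.2 | Counts in 18.4.1 numeric limb |
|---|---|---|---|
| Mild or moderate, 7 days or less, not judged significant | Yes | No | No under either |
| Severe, 7 days or less, not judged significant | Yes | No | Yes under 13.1.7; no under 15.2.2 |
| Severe, 7 days or less, judged significant | Yes | Yes | Yes under both |
| Past 7 days and judged significant | Yes | Yes | Yes under both |

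The first two rows differ in the TEAE tables. Only the second differs in the stopping count. Related SAEs enter through their own limb.

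**Step 3. Illustration for the stopping count.** Let p be the proportion of subjects with a reaction of the second kind. The documents give no such rate, so p is assumed. With n subjects,

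P(at least 2) = 1 − (1 − p)^n − n·p·(1 − p)^(n − 1).

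Take n = 2 × 41 = 82 for the FLU-v arms, or n = 3 × 41 = 123 for all arms, since relatedness is judged blind and placebo contains the adjuvant. For n = 82 and p = 0.01: 1 − 0.4386 − 0.82 × 0.4431 = 0.198.

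| Assumed p | n = 82 | n = 123 |
|---|---|---|
| 0.5% | 6% | 13% |
| 1% | 20% | 35% |
| 2% | 49% | 71% |
| 5% | 92% | 99% |

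These are the chances that such reactions alone would meet the limb if 13.1.7 governs. If 15.2.2 governs, they add 0. The figures use the 18.4.1 wording; the extra synopsis conditions would lower them.

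**Step 4. Who can drop out of both sets of tables?** Take a subject with a severe reaction of 7 days or less who is not challenged. The ITT diary tables exclude this subject. Under 15.2.2 the reaction, unless judged significant, is not an individual AE, so it is not in the Safety-set TEAE tables. What remains is the diary listing, 16.2.5.3. SAP 5.7 points the same way: it keeps unchallenged participants out of the analyses and puts their data in safety listings. Protocol 7.5 replaces subjects withdrawn before challenge, so this group can grow without limiting the challenged sample.

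For scale, FLU-v-002 vaccinated 32 subjects and quarantined 28, so 4/32 = 12.5% did not reach quarantine. If that proportion applied here (an assumption), challenging 123 would need 123 × 32/28 = 140.6, about 141 vaccinated, of whom about 18 would be outside the ITT set.

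**The case against.** The strongest reply is that the two sections can be read together: symptoms are *classified* and graded under 13.1.7, but not *reported individually* under 15.2.2, which is the more specific rule. The SAP fits that reading, since it keeps a diary summary apart from the TEAE tables and the protocol lists diary events as a separate secondary endpoint. This is plausible, but no section states it, and SAP 5.6 does not say that diary symptoms are left out of TEAEs.

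Several stronger readings are tempting and should be set aside:

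- *Severe short reactions can never become AEs.* The test in 15.2.2 is clinical significance in the opinion of the investigator and/or SME, with duration past 7 days as its explanation. A short reaction can still be judged significant.
- *Such reactions are invisible to the stopping provisions.* Only one numeric limb is affected. The SAE limb, the pattern-of-symptoms review in Table 18-1 (Status 2) and the general power to stop in 18.4 do not depend on the conflict.
- *Under 13.1.7 nearly every subject in every arm would have a TEAE, so the Fisher test would tell nothing.* The 32 of 32 subjects with AEs in FLU-v-002 covers a whole challenge study, with 1 mL given in the forearm; this trial gives 0.5 mL in the upper arm. SAP 5.6 also summarises by organ class and preferred term.
- *Cards returned only at the next visit mean that the rules are applied differently between subjects.* The timing of return does not show this.

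It is also fair that severe reactions were scarce before: FLU-v-001 reported no severe local reactions, and FLU-v-002 had one severe AE, on placebo. Both were single-dose studies, so they do not bound the rate after two doses. Finally, the SAP already describes inoculations as done, so new protocol wording may come too late to alter conduct. That limits what the protocol change can achieve, but not the need to define the tables.

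**Conclusion.** The contradiction stands. A stated safety endpoint has two definitions, and no section clearly gives one of them precedence. The effect on the TEAE tables is broad, because every short diary reaction not judged significant is in or out according to the section followed. The effect on stopping is narrow: it concerns severe, related reactions of 7 days or less that nobody judged significant, where two affected subjects give a count of 2 or 0. How often that would matter depends on a rate the documents do not supply; between assumed rates of 0.5% and 5% the chance runs from 6% to 92% among 82 FLU-v subjects.

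Diary reactions are not lost, since they are tabulated by arm, injection and severity. The remaining reporting gap is the analysis set: a vaccinated but unchallenged subject with a severe short reaction could be absent from both the diary and the TEAE tables. The primary endpoint is not touched.

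**What to change.** 1. **Protocol.** The sponsor must reconcile 13.1.7, 15.2.2 and 18.4.1, and the differing stopping text in the synopsis, so that one rule says when a diary symptom is an AE and whether it enters the 18.4.1 count. No view is offered here on which rule that should be. If vaccination is complete, document which rule the site applied.
2. **SAP 5.6.** State which rule the TEAE tables use, and whether diary symptoms are included, excluded, or included only when judged significant.
3. **Tables.** Produce 14.2.2.11.1 and 14.2.2.11.2 on the Safety set as well as ITT, with a row for subjects with any severe diary reaction, by arm and injection, whether or not it was entered as an AE. Square SAP 5.7 with Section 5 so that unchallenged subjects can appear in these tables.

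The cost is wording in two documents and one extra Safety-set presentation. SAP 5.4 already requires diary data by severity, so nothing new has to be collected.

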15.2.3 Complete Physical examination

Any clinically significant change in complete physical examination findings during the study will be documented as an AE.

15.2.4 Directed physical examination

Following Viral Challenge, upper and lower respiratory symptoms (nasal discharge, otitis, pharyngitis, sinus tenderness, new wheezes, râles and rhonchi) will be expected and presumed to represent virus infection consequent to Viral Challenge and will not be additionally captured as AEs unless they meet the definition of an AE, and are deemed to be clinically significant (in the opinion of the Investigator) to be classed as AEs.

Following Viral Challenge all unexpected (in the opinion of the Investigator) post-Viral Challenge directed physical examination findings will be captured as AEs, along with all other occurrences that meet the criteria for an AE.

15.2.5 Vital signs

Deterioration in a vital sign (compared to baseline) should only be reported as an AE if the deterioration fulfils the criteria for an AE. If deterioration in a vital sign is associated with clinical signs and symptoms, the sign or symptom will be reported as an AE and the associated vital sign will be considered as additional information.

15.2.6 Temperature

Following Viral Challenge, pyrexia will be expected and presumed to represent virus infection consequent to Viral Challenge, and will not be additionally captured as an AE unless it meets the definition of an AE, and is deemed to be clinically significant (in the opinion of the Investigator) to be classed as an AE.

Following Viral Challenge all unexpected (in the opinion of the Investigator) post-Viral Challenge pyrexia will be captured as an AE, along with all other occurrences that meet the criteria for an AE.

15.2.7 Spirometry

A 15% drop in a spirometry value (compared to baseline) will be a Grade 1 (mild) AE. The PI will use his/her clinical judgement to assign severity to drops in spirometry values of greater than 15%, based on evaluation of clinical signs and symptoms.

15.2.8 Laboratory values

Deterioration in a laboratory value (compared to baseline) should only be reported as an AE if the deterioration fulfils the criteria for an AE and it is clinically significant in the opinion of the

Investigator. If deterioration in a laboratory result is associated with clinical signs and symptoms, the sign or symptom will be reported as an AE and the associated laboratory result will be considered as additional information.

The Investigator will judge whether abnormal laboratory values are clinically significant or not clinically significant, and record this in the source document. This entry should be signed and dated by the relevant investigator. Laboratory abnormalities detected at screening will be considered as part of the medical history and will not be reported as AEs.

Challenge Virus associated laboratory abnormalities (e.g., elevated ALT, AST or GGT; decreased neutrophils) may be recorded as AEs (at the discretion of the Investigator).

Any laboratory abnormality that meet the criteria of a Grade 2 AE or above will be discussed with the SME. If a Grade 3 laboratory abnormality occurs (not related to Viral Challenge), a confirmatory test should be performed, preferably within 48 hours (if practically feasible) after the results have become available.

15.2.8.1 C-reactive protein

Any value above 5 mg/L but less than 60 mg/L will be a Grade 1 (mild) AE (unless deemed non clinically significant by the PI). The PI will use his/her clinical judgement to assign severity grades above Grade 1, based on evaluation of clinical signs and symptoms.

15.3 Classification of adverse events

15.3.1 Seriousness

The PI must record whether the AE meets the definition of serious. If the event is serious (Section 15.3.1), the PI must initiate reporting to the Sponsor and complete a SAE report form (Section 15.4).

15.3.2 Severity

The term 'severe' is often used to describe the intensity (severity) of a specific event. This is not the same as 'serious' which is based on subject/event outcome or action criteria.

Appendix 4: Division of Microbiology and Infectious Diseases (DMID) Adult Toxicity Table November 2007) will be used to standardise the severity and grading of AEs and anatomical/ pathophysiological terms.

The PI will use these tables as a reference when collecting, reporting and clarifying database queries of AEs, SAEs and ARs.

The severity of an AE that does not appear in the DMID tables should be determined according to the definitions in Table 15-1.

Table 15-1: Classification of adverse event severity

Grade	Classification	Definition
Grade 1	Mild	Mild level of discomfort, and does not interfere with regular activities
Grade 2	Moderate	Moderate level of discomfort and significantly interferes with regular activities
Grade 3	Severe	Significant level of discomfort and prevents regular activities

The DMID AE severity Grade 4 (life threatening) will not be used when assessing AE severity in this trial, because the term 'life threatening' does not relate to severity but to consequence. AEs can be classed, as 'life threatening', and all life threatening AEs must be reported to the Sponsor and NIH as SAEs (as per the definition of a SAE). DMID is a draft internationally recognised tool and is used as best practice guidance.

15.3.3 Frequency

The frequency of the AE should be categorised as one of the following:

- Single
- Intermittent
- Continuous.

15.3.4 Relationship

The relationship of an AE to the IMP will be categorised as shown in Table 15-2.

Table 15-2: Classification of adverse event relationship

Classification	Definition
Not related	The AE is related to an aetiology other than the IMP (the alternative aetiology must be documented in the subject's medical record).
Unlikely to be related	The AE is unlikely to be related to the IMP and likely to be related to factors other than IMP.
Possibly related	There is an association between the AE and the administration of the IMP, and there is a plausible mechanism for the AE to be related to the IMP, but there may also be alternative aetiology, such as characteristics of the subject's clinical status or underlying disease.

Probably related	A reasonable temporal sequence of the AE and the IMP administration exists and, based upon the known pharmacological action of the drug, known or previously reported adverse reactions to the drug or class of drugs, or judgment based on the investigator's clinical experience, the association of the AE with the IMP seems likely.
Definitely related	A definite causal relationship exists between the AE and the administration of the IMP, and other conditions do not appear to explain the AE.

Unless an AE is 'definitely related' to the IMP, a causal relationship to one of the following should be considered, and full details provided on the AE reporting form as appropriate.

- Challenge Virus
- Study procedures
- Concomitant medication
- Other.

15.3.5 Action taken

The Investigator should ensure that adequate medical care is provided to subjects for any AEs, including clinically significant laboratory values related to the IMP. In addition, the Investigator will describe whether any treatment was given for the AE.

The Investigator will classify the action taken with regard to the AE. The action taken should be classified according to the following categories and full details provided as appropriate:

- None
- Non-drug therapy given
- Concomitant medication taken
- IMP dose not changed
- IMP dose adjusted
- IMP administration temporarily interrupted
- IMP administration permanently discontinued
- Subject withdrawn
- Subject hospitalised
- Other.

